### **9.2.2 Visit 2 (Day 1, Randomization)**

This visit will occur 28 days after Visit 1. A visit window of +3 days from the scheduled visit date is permitted, but it is preferred that the visit is performed on the scheduled visit day where possible. Patients will be instructed to record the dosing time of their concomitant AEDs in the diary. They will also be asked to record their meal times the day before and the day of Visit 2.

The following assessments will be made at Visit 2: vital signs, postural blood pressure, physical examination (including height and body weight), details of menstruation (for females), Tanner Staging (for patients aged 10–17 [inclusive], or earlier if clinically indicated by onset of menarche or other signs of precocious puberty) and ECG. Clinical laboratory samples (blood and urine [where possible]) will be taken for hematology, biochemistry, urinalysis, a urine THC screen, determination of serum IGF-1 levels and a pregnancy test, as appropriate (using both a serum sample and urine dipstick test). The patient's IVRS report and paper diary will be reviewed and the information recorded along with information regarding AEs, epilepsy-related hospitalizations, concomitant medications and/or changes to medication (including AEDs).

The investigator must assess the patient's daily number of convulsive seizures from the patient's IVRS data. Patients who have experienced four or more convulsive seizures (i.e., tonic-clonic, tonic, clonic, atonic seizures) during the first 28 days of the baseline period, and who meet all of the other inclusion and none of the exclusion criteria specified in [Section 6](#), will be eligible to continue in the study. If a patient does not meet the eligibility criteria within this period, consideration will be given to rescreen at a later date.

Eligible patients will then be randomized to receive GWP42003-P 10 mg/kg/day, GWP42003-P 20 mg/kg/day, placebo 10 mg/kg/day dose volume equivalent, or placebo 20 mg/kg/day dose volume equivalent at a 2:2:1:1 ratio using the IVRS (see [Section 7.1](#)).

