### **13.1 Sample Size, Power and Significance Levels**

A total of 186 patients will be randomized to one of four treatment groups (GWP42003-P 10 mg/kg/day, GWP42003-P 20 mg/kg/day, placebo 10 mg/kg/day dose volume equivalent, or placebo 20 mg/kg/day dose volume equivalent) at a 2:2:1:1 ratio. The randomization will be stratified by age group (2–5 years, 6–12 years and 13–18 years). The placebo groups will be pooled for the analyses of efficacy.

For a Wilcoxon–Mann–Whitney test comparing two distributions with a two-sided significance level of 0.05, a sample size of 62 per group is required to obtain a power of at least 80%. This is based on a gamma distribution for the GWP42003-P groups with scale parameter of 65.614 and shape parameter of 1.0886, and a gamma distribution for the placebo group with scale parameter of 40.887 and shape parameter of 2.3059.

Maximum likelihood estimates using the Newton–Raphson approximation were computed for the scale and shape parameters using data from study GWEP1332 Part B.

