  - MI will be performed on the convulsive seizure frequency, based on time-points corresponding to each 14 calendar days of the treatment period. Intermittent missing values for intermediate 14-day time-points before the last 14-day time-point will be imputed using the MCMC method in SAS PROC MI with an IMPUTE=MONOTONE statement for 100 times for each treatment group separately. Then, monotone missing data assumed under the MAR assumption at time-point  $t$  (i.e., patients in the placebo group and patients in the GWP42003-P groups who did not discontinue due to AEs or for any reason) will be imputed using the MI procedure with the ‘MONOTONE REG’ option, for each treatment group separately. The imputation model will include baseline convulsive seizure frequency and each 14-day time-point up to time-point  $t$  (in chronological order). With the data imputed from above, monotone missing data of patients in the GWP42003-P groups under the MNAR assumption will be imputed. At each 14-day time-point  $t$ , the input dataset for the MI procedure will include all placebo patients and those patients from the GWP42003-P groups that have values missing under MNAR at that time-point. The imputation model will include convulsive seizure frequency at baseline and each 14-day time point up to time-point  $t$  (in chronological order) and will be performed for each GWP42003-P group separately.

Full details for this sensitivity analysis will be provided in the SAP.

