### 5.5.2 Primary Efficacy Endpoint

The primary endpoint is the change in convulsive seizure frequency during the treatment period (see Section 5.1.3.3) of the study compared to baseline (see Section 5.1.3.1) in patients taking GWP42003-P compared with placebo.

The primary endpoint will be analyzed using negative binomial regression on the sum of the convulsive seizure counts during the treatment period. However, convulsive seizure frequency (28-day average) and percentage change in seizure frequency will be presented using summary statistics. Percentage change from baseline in convulsive seizure frequency will be calculated as:

$$\frac{[(\text{Frequency during the treatment period} - \text{Frequency during baseline}) \div \text{Frequency during baseline}] \times 100}{}$$

The frequency during each period will be based on 28-day averages and calculated as:

$$(\text{Number of seizures in the period} \div \text{Number of reported days in IVRS in the period}) \times 28$$

For convulsive seizure endpoints only, if patients are randomized with no convulsive seizures during the baseline period then the percentage change from baseline will be calculated as:

---

(Frequency during the treatment period + 1) × 100

A mixed effect model with repeated measures will be performed modelling the observed number of convulsive seizures in the baseline period and treatment period implemented within the framework of general linear models using the negative binomial response distribution. The model will include stratified age group (2–5 years, 6–12 years and 13–18 years), time, treatment arm and treatment arm by time interaction as fixed effects and patient as a random effect. The log transformed number of days in which seizures were reported will be included as an offset. The time variable corresponds to an indicator for the baseline period and treatment period.

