- Step 1: Monotone missing data under the MAR assumption at treatment period time-point t will be imputed by means and covariance from the observed convulsive seizure frequency at baseline and at each treatment period time-point up to time-point t (in chronological order) in their corresponding treatment groups (i.e., patients in the GWP42003-P groups whose missing data are assumed to be MAR and all patients in the placebo group). The imputation will be realized using the MI procedure with the 'MONOTONE REG' option, for each treatment group separately. The imputation model will include baseline convulsive seizure frequency and each treatment period time-point up to time-point t (in chronological order).
- Step 2: With the data imputed from Step 1, monotone missing data of patients in the GWP42003-P groups under the MNAR assumption will be imputed. At each treatment period time-point t, the input dataset for the MI procedure will include all placebo patients and those patients from each GWP42003-P group that have values missing under MNAR at that time-point. The imputation model will include convulsive seizure frequency at baseline and each treatment period time-point up to

time-point  $t$  (in chronological order). After the sequential imputation is completed for all time-points, the imputed values at time-point  $t$  plus, a sensitivity parameter,  $k \times$  standard error of the observed convulsive seizure frequency in the placebo group at the corresponding time-point (calculated using the denominator of the total number of reported days in IVRS for all combined periods, as given above) will then form the final imputed values. The sensitivity parameter  $k$  (where, for example,  $k = 0, \pm 0.5, \pm 1.0, \pm 1.5$ , etc.) will be used to explore the robustness of the estimated treatment difference to the degree of decrease or increase (positive values of  $k$  represent decrease and negative values represent increase) in MNAR efficacy from the placebo patients.

After missing values at all the time-points are imputed, the overall percentage change from baseline in convulsive seizure frequency will be calculated as:

$$\left[ \frac{\text{The sum of the frequencies of each 14 days of the treatment period} - \text{Frequency during baseline}}{\text{Frequency during baseline}} \right] \times 100$$

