If the sum of the frequencies of each 14 days of the treatment period becomes less than zero, as a result of imputation, then the percentage change from baseline in convulsive seizure frequency will be set to  $-100\%$ .

The data will then be analyzed using a Wilcoxon rank-sum test.

The results of the Wilcoxon rank-sum test on the 100 imputed datasets will be combined to derive an overall p-value. The test statistic will be based on the method provided by Rubin and a modified macro from Mogg.

For each analysis, the increment in the positive value of  $k$  will stop once the overall p-value is greater than 0.05. The decrease in the negative values of  $k$  will continue until the overall p-value becomes smaller than the p-value from the primary efficacy analysis, for the corresponding Dose Level.

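### The dropout sensitivity analysis imputes skewed seizure frequencies with unbounded normal models and corrects negatives only in the patient total, which blunts the tipping-point penalty

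*SAP*

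**What the plan says.** SAP 5.5.2.1.1 splits the treatment period into seven 14-day blocks (the last has 15 days). It expresses each block as a frequency over the patient's total reported days, so that the seven values add up to the overall 28-day rate. Missing blocks are filled in three moves:

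- Gaps before the last observed block: PROC MI with MCMC, 100 times, by treatment group.
- Blocks after dropout assumed missing at random: "The imputation will be realized using the MI procedure with the" MONOTONE REG option, again by group.
- Blocks after dropout assumed not missing at random in the active groups: the same type of sequential model, fitted with the placebo patients. Then k times the placebo standard error is added, positive k meaning a worse outcome.

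Protocol 13.6.2.1 describes the same model ("The imputation model will include baseline convulsive seizure frequency and each 14-day time-point up to time-point" t) and leaves full details to the SAP. Neither document states a transformation, a minimum or a per-block truncation. The one rule for negatives acts on the seven-block total: "If the sum of the frequencies of each 14 days of the treatment period becomes less than zero, as a result of imputation", the percentage change becomes −100%. A Wilcoxon test follows, pooled over imputations, and positive k is increased until the pooled p-value exceeds 0.05.

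Elsewhere the plan treats this outcome as skewed. The primary model is "implemented within the framework of general linear models using the negative binomial response distribution" (SAP 5.5.2), one sensitivity analysis log-transforms it (SAP 5.5.2.1), and the sample size rests on gamma distributions (Protocol 13.1).

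**The concern.** MCMC in PROC MI and MONOTONE REG both draw from normal models. Applied to a skewed variable that cannot fall below zero, they produce negative seizure frequencies, and the SAP's rule shows that its authors expected this. The rule catches only the extreme case. A negative block inside a positive total stays in and subtracts from seizures the caregiver reported. When the total does fall below zero, a patient who dropped out ties with patients who were truly seizure free.

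The other analyses do not fill this gap. The LOCF/NOCB analysis covers unreported diary days, and the primary analysis uses the data available before withdrawal. What is at stake is therefore whether the tipping-point k can be read as the size of penalty the result withstands.

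**Working it through.** **1. The plan's own figure.** Protocol 13.1 states "a two-sided significance level of 0.05, a sample size of 62 per group is required to obtain a power of at least 80"%. The active assumption is "a gamma distribution for the GWP42003-P groups with scale parameter of 65.614 and shape parameter of 1.0886", so the mean (shape × scale) is 1.0886 × 65.614 = 71.4 and the skewness (2/√shape) is 1.92. The placebo assumption is "a gamma distribution for the placebo group with scale parameter of 40.887 and shape parameter of 2.3059", so the mean is 2.3059 × 40.887 = 94.3 and the skewness is 1.32. P(active < placebo) = 0.643 by numerical integration. Simulated power at 62 per group is 79.96% (20,000 trials, Monte Carlo standard error about 0.3 points). Noether's formula gives N = (1.960 + 0.842)² / [12 × 0.25 × (0.643 − 0.5)²] ≈ 127.5, or 64 per group. The stated figure is reproduced, and the planning distributions are clearly skewed.

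**2. The algebra.** Let O be the sum of a patient's observed block frequencies, I the sum of the imputed ones and B the baseline. The score is 100 × (O + I − B)/B, and the rule acts only if O + I < 0. If −O < I < 0, nothing is corrected, and the score is better than 100 × (O − B)/B, the score for having no seizures at all after dropout.

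**3. How often this happens.** The SAP algorithm was simulated with 62 per arm. The gamma parameters were read as percent of baseline. Baseline rates were lognormal and truncated at four per 28 days, following the entry rule ("Patients who have experienced four or more convulsive seizures"). Dropout time was uniform. Baseline spread, dispersion and dropout rates are assumptions. The last three columns are shares of dropout patients or of their imputations.

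| Baseline median, log-SD, dispersion | Active dropout | k | Imputed blocks < 0 | I < 0 with seizures recorded | Scored −100% | True total zero |
|---|---|---|---|---|---|---|
| 12, 0.5, 0.2 | 10% | 0 | 23.8% | 15.1% | 10.8% | 3.3% |
| 12, 0.8, 0.5 | 10% | 0 | 27.2% | 17.3% | 13.7% | 3.6% |
| 20, 1.0, 0.5 | 10% | 0 | 29.2% | 21.8% | 15.7% | 1.4% |
| 12, 1.2, 0.5 | 10% | 0 | 30.1% | 21.5% | 16.8% | 3.1% |
| 12, 1.2, 0.5 | 20% | 0 | 31.1% | 22.7% | 18.0% | 2.9% |
| 12, 1.2, 1.0 | 10% | 0 | 32.4% | 23.2% | 20.9% | 5.0% |
| 12, 1.2, 0.5 | 10% | +2 | 17.7% | 9.7% | 6.9% | 1.9% |
| 12, 1.2, 0.5 | 10% | +5 | 7.4% | 2.4% | 1.5% | 3.9% |

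Two further simulations under other assumed settings gave 22–28% and 28–32% negative blocks, and 9–22% and 15–21% scored −100%, at k = 0.

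**4. Effect on the test.** Mean pooled Wilcoxon Z (150 data sets, 20 imputations; more negative favours active):

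| Setting as above | Dropout, active/placebo | k | SAP rule | Same draws, each block floored at 0 | Log-scale imputation | No missing data |
|---|---|---|---|---|---|---|
| 12, 1.2, 0.5 | 10%/3% | 0 | −2.295 | −2.221 | −2.393 | −2.501 |
| 12, 1.2, 0.5 | 20%/5% | 0 | −2.183 | −2.004 | −2.327 | −2.537 |
| 12, 0.8, 0.5 | 15%/5% | 0 | −2.349 | −2.263 | −2.418 | −2.601 |
| 12, 0.5, 0.2 | 15%/5% | 0 | −2.425 | −2.387 | −2.462 | −2.597 |
| 12, 1.2, 0.5 | 20%/5% | +2 | −1.648 | −1.572 | −1.502 | −2.524 |

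In the k = 0 rows, the share scored −100% falls from 10.2–18.5% under the SAP rule to under 1% with either alternative. The SAP rule differs from log-scale imputation by 0.04–0.14 and is slightly less favourable to active. A separate simulation that included predictive mean matching gave 0.01–0.11.

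At k = +2 the order reverses. The SAP rule is 1.648 − 1.502 = 0.146 more favourable to active here, and 0.06–0.22 more favourable than log-scale or matching imputation in the separate simulation. In the 20%/5% setting, moving k from 0 to +2 shifts Z by 2.183 − 1.648 = 0.535 under the SAP rule and by 2.327 − 1.502 = 0.825 on the log scale. The nominal penalty thus has about a third less effect (0.535/0.825 = 0.65).

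Linear interpolation between those two points puts the crossover at k = 0.144/(0.4125 − 0.2675) ≈ 1.0.

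**The case against.** The strongest reply is that the final test uses ranks, so the size of an extreme imputed value hardly matters, and that placebo dropouts are imputed with the same kind of model. At k = 0 this largely stands, since Z moves by about 0.1 and in the direction unfavourable to active. The share scored −100% also falls as k rises. It does not remove the reversal at k = +2.

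The obvious repair, a zero floor on raw normal draws, is not neutral either. It discards negative draws and keeps positive ones. In one check it raised the mean imputed block by 22–32% and moved Z against active by 0.11–0.34. That stands, and it limits the floor to a guard.

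Three stronger readings are tempting, but the documents do not support them:

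- That dropouts as a class are scored as fully improved. The rule applies only to imputations whose total is negative.
- That active dropouts were meant to be no better than placebo. The SAP allows imputed values similar to, below or above placebo's, and has its own stopping rule for negative k. Placebo-like is the k = 0 case only.
- That the trial's conclusion is biased. This is one sensitivity analysis among about ten. The primary negative binomial model and the testing hierarchy do not use these imputations.

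**Conclusion.** The concern holds in a limited form. The mechanism follows from the SAP text: raw-scale normal imputation, no bound per block, correction only of the total. Its frequency rests on assumed baseline spread, dispersion, dropout rates and timing, but the artefact appeared in every setting tried.

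The effect on the Wilcoxon result at k = 0 is small. The harm is at positive k, where the penalty is weakened. In the one setting traced at two values of k, a borderline result would tip at nearly the same k either way: (2.183 − 1.96)/0.2675 ≈ 0.8 under the SAP rule and (2.327 − 1.96)/0.4125 ≈ 0.9 on the log scale. The tipping-point k is overstated for results that survive past about k = 1, which are the results for which robustness would be claimed. The analysis should be corrected because it is the plan's only model of informative dropout. The primary result is not affected.

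**What to change.** Amend SAP 5.5.2.1.1 before unblinding:

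- Run both the MCMC step and the monotone steps on log(frequency + constant) and back-transform. Alternatively, use log-scale MCMC for intermittent gaps and MONOTONE REGPMM for the monotone steps. Matching alone does not cover the MCMC step.
- Pre-specify the constant. Block values are small: with an assumed baseline of 12 per 28 days, a block averages 12/7 ≈ 1.7, so the 1 used in the log ANCOVA would be large here. The simulations used 0.1.
- Truncate each imputed block at zero after back-transformation and again after adding k × SE, as a guard only.
- Report how many imputed values and patient totals hit the bound, by group and k.

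The cost is a few lines of SAS and SAP wording. The protocol already defers these details to the SAP. The downsides are small: matching draws only from observed values, so extremes are slightly narrower, and the log route adds a constant to justify.

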### 5.5.3 Secondary Efficacy Endpoints

#### 5.5.3.1 Key Secondary Efficacy Endpoints

##### 5.5.3.1.1 1st Key Secondary Endpoint: Total Seizures

Summaries and analyses of total seizures (see Section 5.1.3.7) will be performed as per the primary endpoint (Section 5.5.2).

The analysis will be performed on the ITT analysis set and repeated on the PP analysis set.

Sensitivity analyses will be performed on the ITT analysis set, repeating the above analysis, using data for only the maintenance period, and during each 4 weeks of the maintenance period (Week 1–4, Week 5–8 and Week 9–12 of the 12-week maintenance period).

Analyses on the maintenance period and by each 4 weeks of the maintenance period will include only patients who have at least 7 days of seizure data within each corresponding period.

### **5.5.3.1.2 2nd Key Secondary Endpoint: Convulsive Seizure Treatment Responders (≥50% Reduction in Convulsive Seizure Frequency)**

The proportion of patients considered treatment responders, defined as those with a ≥50% reduction in convulsive seizure frequency from baseline, during the treatment period, will be summarized by treatment group and analyzed using a Cochran–Mantel–Haenszel (CMH) test stratified by age group.

The proportion of patients who are considered treatment responders, the difference in proportions along with the 95% CI for the difference, the estimated odds ratios (GWP42003-P groups vs. placebo), 95% CI for the odds ratios, and the p-values from the CMH test will be presented. If no patients in a particular treatment group are considered responders then the odds ratio and 95% CI for the odds ratio will not be calculated.

The analysis will be performed on the ITT analysis set and repeated on the PP analysis set.

Sensitivity analyses will be performed on the ITT analysis set, repeating the above analysis, using data for the maintenance period only, and during each 4 weeks of the maintenance period (Week 1–4, Week 5–8 and Week 9–12 of the 12-week maintenance period).

Analyses on the maintenance period and by each 4 weeks of the maintenance period will include only patients who have at least 7 days of seizure data within each period.

### **5.5.3.1.3 3rd Key Secondary Endpoint: Caregiver Global Impression of Change**

The CGIC will be assessed at Visits 3, 4, 6 and 8 (end of treatment). The CGIC comprises the following question to be rated on a 7-point scale:

- Since your child started treatment, please assess the status of your child's overall condition (comparing their condition now to their condition before treatment) using the scale below.

The possible responses are: Very Much Improved; Much Improved; Slightly Improved; No Change; Slightly Worse; Much Worse; Very Much Worse.

The responses above are based on comparison with a brief description of the patient's overall condition used as a memory aid from Visit 2.

Each response will be coded with a score from 1 to 7, where 1 = Very Much Improved, and 7 = Very Much Worse.

The CGIC response/score, recorded at each visit, will be summarized, on both a categorical and continuous scale, by treatment group.

The score at the end of treatment visit and last visit (if different to the end of treatment) will be analyzed using ordinal logistic regression. Proportional odds modelling will be carried out by including treatment group as a factor. The estimated odds ratios (GWP42003-P arms vs. placebo), 95% CI for the odds ratios, and the p-value testing the null hypothesis that the odds ratio is equal to 1, will be presented. Analysis performed at the last visit will be considered the main analysis for this endpoint, with the analysis at the end of treatment visit considered a sensitivity analysis.

Should the proportional odds assumption not hold, i.e. if the p-value for the score test for proportional odds assumption is <0.05, then, as a sensitivity analysis, the scores will also be analyzed using a Cochran-Armitage trend test. This will be presented together with the results of the ordinal logistic regression.

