For number of hospitalizations due to epilepsy, sleep disruption, daytime sleepiness, QOLCE, cognitive function and behavior assessments, the data will be summarized at baseline, over the treatment period, and at each time point (or 28-day period, as appropriate) during the maintenance period. Changes from baseline to the average over the treatment period (or at the end of study) will be analyzed using ANCOVA (or appropriate non-parametric methods if data are found to be not normally distributed). The model will include baseline (where applicable) and age group as covariates and treatment group as a fixed factor. The estimated least squares means, treatment difference, together with the 95% CIs and p-value will be presented.

For changes in non-convulsive and total seizure frequency and changes in frequency of other seizure types the data will be summarized at baseline, over the treatment period, and at each time point (or 28-day period, as appropriate) during the maintenance period. Changes over the treatment period compared to baseline will be analyzed using the same analysis as the primary endpoint.

CGIC and CGICSD assessments recorded at the end of treatment will be analyzed with ordinal logistic regression using the proportional odds model.

Changes from baseline for IGF-1 levels will be summarized by treatment group and plotted against the Tanner Stages, weight, and height.

Tanner Stages will be evaluated and summarized descriptively at each time point in terms of frequency and proportions. Number (%) of patients with changes in Tanner Stages and the transition time between stages will be summarized by treatment group.

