#### **3.2 Definition of Sample Size**

A total of 186 patients will be randomized to one of 4 treatment groups (GWP42003-P 10 mg/kg/day, GWP42003-P 20 mg/kg/day, placebo 10 mg/kg/day dose volume equivalent, or placebo 20 mg/kg/day dose volume equivalent) at a 2:2:1:1 ratio. The randomization will be stratified by age group (2–5 years, 6–12 years and 13–18 years). The placebo groups will be pooled for the analyses of efficacy.

For a Wilcoxon–Mann–Whitney test comparing 2 distributions with a 2-sided significance level of 0.05, a sample size of 62 per group is required to obtain a power of at least 80%. This is based on a gamma distribution for the GWP42003-P groups with scale parameter of 65.614 and shape parameter of 1.0886, and a gamma distribution for the placebo group with scale parameter of 40.887 and shape parameter of 2.3059.

Maximum likelihood estimates using the Newton–Raphson approximation were computed for the scale and shape parameters using data from study GWEP1332 Part B.

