### **5.5 Efficacy Analysis**

#### **5.5.1 General Approach**

The primary analyses will use the ITT analysis set. Further analyses using the PP analysis set will also be performed for the primary endpoint and secondary endpoints where specified in the sections below.

The primary null hypothesis is:

- Following 14 weeks of treatment there is no difference in effect between the 20 mg/kg/day GWP42003-P treatment group and the placebo treatment group in terms of the change in convulsive seizure frequency during the treatment period compared to baseline.

The null hypothesis will be rejected if there is statistical evidence of a difference between the treatment groups at the  $\alpha$ -level of 0.05 for the primary endpoint.

Statistical hypothesis testing will be performed on the primary endpoint and other endpoints as appropriate. Each endpoint, including the primary will have 2 comparisons against placebo (20 mg/kg/day GWP42003-P and 10 mg/kg/day GWP42003-P vs. placebo). Also, 3 key secondary endpoints have been defined.

The primary and key secondary endpoints will be tested with their Type I error controlled by use of a hierarchical gate-keeping procedure, in the sequence given in Table 3. One must reject the null hypothesis of an endpoint at the level of 0.05 (2-sided) to test the hypothesis of the subsequent endpoint in the sequence at the level of 0.05 (2-sided). If a null hypothesis is not rejected then testing will stop and all subsequent analyses will be declared not statistically significant.

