#### 5.5.3.2.5 Caregiver Global Impression of Change in Seizure Duration

The CGICSD comprises the following question to be rated on a 3-point scale for each seizure type:

- Since the patient started treatment, please assess the average duration of the patient's seizures (comparing their condition now to their condition before treatment) using the scale below.

The 3 possible responses are:

- Decrease in average duration.
- No change in average duration.
- Increase in average duration.

The caregiver will be asked to assess the average duration of the patient's seizures at Visit 2 (prior to commencement of IMP) as a memory aid for assessment at the end of treatment visit.

Each response will be coded with a score from 1 to 3, where 1 = Decrease in average duration, and 3 = Increase in average duration.

For each seizure type, the CGICSD will be summarized by treatment group and analyzed using ordinal logistic regression.

Proportional odds modelling will be carried out by including treatment group and age group as factors. The estimated odds ratios (GWP42003-P groups vs. placebo), 95% CI for the odds ratios, and the p-values testing the null hypothesis that the odds ratio is equal to 1, will be presented.

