**Table 6 Adaptive Levels by v-Scale Scores and Standard Scores**

Adaptive Level	v-Scale Score for Subdomains and Maladaptive Behavior Index	Standard Score for Domains and Adaptive Behavior Composite
Adaptive Behavior Domains		
Low	1 to 9	20 to 70
Moderately Low	10 to 12	71 to 85
Adequate	13 to 17	86 to 114
Moderately High	18 to 20	115 to 129

High	21 to 24	130 to 160
Maladaptive Behavior Domain		
Clinically Significant	21 to 24	
Elevated	18 to 20	
Average	1 to 17	

The v-scale score from the 11 adaptive behavior subdomains, 3 maladaptive behavior subdomains and the maladaptive behavior index, and the standard score from the 4 adaptive behavior domains and the adaptive behavior composite, recorded at each visit, will be summarized, on a continuous scale, by treatment group. The change from baseline (Visit 2) will also be included.

The change from baseline to the end of treatment visit and last visit (if different to the end of treatment), for the 4 adaptive behavior domains, the adaptive behavior composite and the maladaptive behavior index only, will be analyzed using the same ANCOVA approach as specified in Section 5.5.3.2.7. Analysis performed at the last visit will be considered the main analysis for this endpoint, with the analysis at the end of treatment visit considered a sensitivity analysis.

The adaptive level from the 11 adaptive behavior subdomains, 4 adaptive behavior domains, the adaptive behavior composite, the 3 maladaptive behavior subdomains and the maladaptive behavior index, recorded at each visit, will be summarized, on a categorical scale, by treatment group.

The adaptive level from the 4 adaptive behavior domains, the adaptive behavior composite and the maladaptive behavior index only will be analyzed using ordinal logistic regression. Factors for treatment and age group will be included along with the baseline adaptive level as a covariate. The estimated odds ratios (GWP42003-P groups vs. placebo), 95% CI for the odds ratios, and the p-values testing the null hypothesis that the odds ratio is equal to 1, will be presented.

Each adaptive level for adaptive behavior will be coded with a score from 1 to 5, where 1 = Low, and 5 = High. Each adaptive level for the maladaptive behavior index will be coded with a score from 1 to 3, where 1 = Clinically Significant, and 3 = Average.

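### The CGIC model (tests 7 and 8) is the only alpha-controlled analysis that leaves out age group, the randomization stratum; adding it costs almost nothing and recovers power if age predicts CGIC

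*SAP*

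**What the plan says.** SAP 3.2 names one stratification factor: "The randomization will be stratified by age group", in three bands. SAP 5.5.1 puts four endpoints, each with two dose comparisons, under strong control: "The primary and key secondary endpoints will be tested with their Type I error controlled by use of a hierarchical gate-keeping procedure". Table 3 of the SAP orders the eight tests, and CGIC takes places 7 and 8.

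How the SAP treats age group in each case:

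- Tests 1 and 2, convulsive seizures (5.5.2): "The model will include stratified age group".
- Tests 3 and 4, total seizures (5.5.3.1.1): analysed by reference to the primary model, so age group is included.
- Tests 5 and 6, 50% responders (5.5.3.1.2): a Cochran–Mantel–Haenszel "test stratified by age group".
- Tests 7 and 8, CGIC (5.5.3.1.3): "Proportional odds modelling will be carried out by including treatment group as a factor". No other term is listed.
- CGICSD, not alpha-controlled (5.5.3.2.5): "Proportional odds modelling will be carried out by including treatment group and age group as factors".
- Vineland-II adaptive levels, not alpha-controlled (5.5.3.2.10): "Factors for treatment and age group will be included along with the baseline adaptive level as a covariate".

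Protocol 13.6.3 covers CGIC and CGICSD in a single sentence with one method and no covariates: "CGIC and CGICSD assessments recorded at the end of treatment will be analyzed with ordinal logistic regression using the proportional odds model".

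**The concern.** When randomization is stratified, the analysis would normally carry the stratification factor, and this SAP does so for every other confirmatory test. CGIC and CGICSD start from the same protocol sentence. The SAP then gives the stratum to the one that is not alpha-controlled and withholds it from the one that is. Where the SAP drops age on purpose, in the age-subgroup model of 5.5.5, it says so. Nothing similar appears in 5.5.3.1.3, in 5.5.1 or in 5.8, so this reads as an oversight.

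What is at stake is efficiency and clarity, not validity. Stratified allocation balances age across arms. If age predicts CGIC, a treatment-only model still counts the age-related spread in its standard error, so the test rejects too rarely under the null and loses power. It also estimates a marginal odds ratio, which lies closer to 1 than the odds ratio conditional on age. That is a different quantity, not a bias, but the confirmatory one should be chosen deliberately. If age adjustment were brought in after unblinding, it would be post hoc.

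**Working it through.** **The plan's own figure.** The documents give no power, effect size or response distribution for CGIC. The only sample-size figure is 62 per group for the Wilcoxon–Mann–Whitney comparison (SAP 3.2). With the stated gamma distributions, P(active < placebo) = 0.643. Noether's formula n = (1.960 + 0.842)² / [6(0.643 − 0.5)²] gives 64 per group using the unrounded probability, and a version using the variance under the alternative gives 63. At 62 per group, power is 78.9%, 79.6% and 79.3% (Noether, alternative variance, simulation). The stated figure is therefore reproduced closely, and it does not depend on the CGIC model. I take 62 per arm from it.

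**Model.** logit P(Y ≤ j) = α_j + β_arm + γ_age, with seven ordered categories, three arms fitted jointly, and a two-sided 5% Wald test of one active arm against placebo, with and without γ_age.

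**Assumptions, none of them in the documents.** The conditional odds ratio is 2.5 in both active arms, chosen to give about 80% power. The age effect is linear across bands.

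- Set A: strata of 18/26/18 per arm; placebo probabilities .03/.12/.25/.40/.12/.06/.02.
- Set B: strata of 19/25/18 per arm; placebo probabilities .06/.12/.22/.38/.12/.07/.03.

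Each scenario has 8,000 replicates. The Monte Carlo standard error is about 0.5 point for power and 0.25 for type I error. Gains are taken before rounding.

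| Age OR, extreme bands | Set B power: treatment only → with age | Set B gain | Set A power: treatment only → with age | Set A gain | Set A null rejection: treatment only / with age |
|---|---|---|---|---|---|
| 1.0 | 81.3 → 81.6% | 0.2 | 80.7 → 81.2% | 0.5 | 5.2 / 5.4% |
| 1.65 | 81.5 → 82.1% | 0.7 | 80.5 → 81.0% | 0.4 | 5.0 / 5.1% |
| 2.7 | 79.7 → 81.2% | 1.6 | 78.8 → 80.6% | 1.8 | 4.9 / 5.5% |
| 4.5 | 77.9 → 81.4% | 3.5 | 78.0 → 81.9% | 3.8 | 4.2 / 5.2% |
| 7.4 | 74.5 → 81.1% | 6.6 | 73.9 → 80.7% | 6.8 | 3.8 / 5.9% |

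Two further placebo distributions gave gains of 0.2–0.4, 1.6–1.9 and 6.2–6.4 points at age odds ratios of 1.0, 2.7 and 7.4.

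**Hand check of the mechanism (set B averages), power ≈ Φ(ln OR / SE − 1.96).**

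- Age OR 2.7, treatment only: ln 2.480 / 0.328 = 2.77, power ≈ Φ(0.81) = 79.1%. With age: ln 2.564 / 0.329 = 2.86, power ≈ Φ(0.90) = 81.6%.
- Age OR 7.4, treatment only: ln 2.298 / 0.326 = 2.55, power ≈ Φ(0.59) = 72.3%. With age: ln 2.538 / 0.329 = 2.83, power ≈ Φ(0.87) = 80.8%.

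The standard errors barely differ. The treatment-only estimate moves toward 1 while its standard error does not shrink to match. The simulated 74.5% exceeds the hand value of 72.3% because the true spread of the treatment-only estimate is smaller than its model standard error. That same gap is what makes the test conservative under the null.

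**The case against.** The strongest reply is that no error has been shown. The treatment-only test is pre-specified, valid and if anything conservative. It is last in the hierarchy, so it can affect no earlier test, and it matters only if tests 1 to 6 all reject. All of this stands.

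Second, SAP 5.8 records changes from the protocol, and the protocol names no covariates for CGIC, so there was no departure to list. This also stands. The point is unexplained inconsistency within the SAP, not an undisclosed deviation.

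Third, the adjusted Wald test runs slightly above 5%, so part of the apparent gain is test size. With the adjusted test calibrated to a true 5% under set A, the gains become −0.2, 0.1, 1.2, 3.3 and 5.3 points at age odds ratios of 1.0, 1.65, 2.7, 4.5 and 7.4. This trims the figures, and it removes essentially all of the gain at weak age effects. It does not reverse the conclusion where age is moderately or strongly prognostic.

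Fourth, the larger gains need a strong age effect on a rating of change against the child's own earlier state, which may be unlikely. That is fair: the documents say nothing about how strongly age predicts CGIC.

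Finally, adjustment adds a proportional-odds assumption for age and changes the reported odds ratio to an age-conditional one. Both should be acknowledged in the SAP. Neither is a reason to keep the stratum out.

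**Conclusion.** The concern holds. CGIC is the only one of the four alpha-controlled endpoints analysed without age group, and the SAP offers no reason. This is a matter of efficiency and consistency; type I error is not inflated.

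Nothing material is lost by adjusting if age is irrelevant to CGIC. If age is prognostic, adjustment recovers about 1 to 2 points of power at an age odds ratio of 2.7, 3 to 4 at 4.5 and 5 to 7 at 7.4, where the lower ends reflect size calibration. These figures rest on the assumed CGIC distributions, stratum sizes, treatment odds ratio of 2.5 and age effects. The textual finding does not depend on any of them.

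**What to change.** Before unblinding, replace the model sentence in SAP 5.5.3.1.3 with the one already used in 5.5.3.2.5: "Proportional odds modelling will be carried out by including treatment group and age group as factors". Apply it to both the last-visit (main) and end-of-treatment analyses. State that tests 7 and 8 use the age-adjusted p-value and that the reported odds ratio is conditional on age group. Keep the treatment-only model as a sensitivity analysis. If age was left out on purpose, give the reason in one sentence instead; 5.8 is a convenient place.

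The cost is one line of SAP text, one extra factor in the model statement and one sensitivity row. Age group is already collected and already used in the other models, so no new data or patients are needed.
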